Title: Spinal Cord Stimulation to Augment Activity Based Therapy
NCT #: NCT03240601
Date: 12/28/2021

Protocol

This study was carried out with the ethics approval from the Shepherd Center Research Review Committee (Project #696). All participants provided written informed consent prior to study enrollment in accordance with the Declaration of Helsinki, and the study was conducted in accordance with HIPAA guidelines. This study was registered with clinicaltrials.gov (NCT03240601).

Subjects

We captured data related to both feasibility of applying TSS as part of a program of usual care LT, as well as data related to the impact of LT+TSS on walking and spasticity measures. Participants were recruited from the inpatient clinical services of a specialty rehabilitation hospital. Recruitment was via advertisements, information provided in a monthly research education class, and information conveyed to potential participants by clinical staff. To be eligible for the study, participants had to be in the subacute rehabilitation phase of the SCI (2-6 months post injury) and had to qualify for participation in a clinical LT program as determined by their physical therapist. Individuals were eligible for participation if they met the following inclusion criteria: 16-65 years of age with SCI, ability to take at least one step with or without an assistive device, and presence of at least mild spasticity affecting the lower extremity muscles (as determined by participant self-report). Individuals with the following exclusion criteria were not considered for participation: neurological level of injury at or below T12, progressive or potentially progressive spinal lesions, (including degenerative or progressive vascular disorders of the spine and/or spinal cord), history of cardiovascular irregularities, difficulty following instructions, orthopedic problems that would prevent participation in study interventions (i.e. knee or hip flexion contractures >10 degrees), women who were pregnant, or had reason to believe may become pregnant, persons who have implanted stimulators/electronic devices of any type, and persons with an active infection of any type.

Study Design

We used a wash-in, randomized, control study design consisting of four consecutive weeks of LT directed by physical therapists. For the first two weeks, participants received 6 bouts of LT. For the last 2 weeks, participants were randomized to receive 6 bouts of either 30 minutes of TSS coupled with LT or a sham-control stimulation coupled with LT. Primary outcome assessments for walking function and spasticity were conducted at the beginning and end of each 2-week intervention block (first 2-weeks [wash-in phase] and second 2-weeks [intervention phase]). The assessments at the end of each 2-week block were performed prior to the training on that day. Pre-post training assessments of spasticity and assessments of tolerability (see below) were performed on each training day.

Intervention

Intervention. LT approaches used in the study included treadmill-based training with or without body weight support and with or without manual or robotic assistance (Lokomat, Hocoma, Volketswil, Switzerland) as well as overground locomotor training with or without body weight support and with or without manual assistance. LT approaches for each participant were chosen by the treating therapist in accordance with standard clinical practice. LT duration was approximately 1 hour and included both setup and take down time of all equipment.

Transcutaneous Spinal Cord Stimulation (TSS). Electrical stimulation (50Hz, biphasic pulses) was applied using a portable electrotherapy device (Empi Continuum, DJO Global, Vista, CA, USA), as previously described (Estes, Iddings et al. 2017). Briefly, with the participant seated, the stimulating electrode (5 cm round electrode) was placed over vertebral levels T11/T12, identified via manual palpation and the reference electrode (10 cm x 15 cm butterfly electrode) was placed over the umbilicus. With the participant standing, the stimulator was turned on and

adjusted to a level at which the participant reported sensations of tingling in the legs and feet or to the highest level the participant could tolerate. participants were standing. For those with impaired sensation as well as those with sensation, target stimulation was subthreshold for lower extremity muscle activation and verified by the absence of visible muscle contraction. Stimulation was delivered for 30 minutes at the target stimulation intensity and occurred concomitantly with LT. Following 30 minutes of stimulation, the intensity was ramped down and the stimulation unit was turned off and disconnected. If LT finished prior to the 30 minutes of stimulation, then participants completed their 30 minutes of stimulation while seated on a high-lo mat where training day assessments would occur. Conversely, if the 30 minutes of stimulation finished prior to the end of LT, then the LT session was completed prior to the assessments.

Sham-control stimulation -- TSSsham. The sham-control was designed to control for placebo effects associated with the perception of intervention. For the TSSsham, a 2-inch round electrode was placed over T11/T12 and a reference electrode was placed over the umbilicus, as performed with TSS. The intensity of electrical stimulation was briefly ramped up to a level at which the participants reported perceiving the stimulation, then ramped down and turned off for the remainder of the intervention. The stimulator and electrodes remained attached to the participant for 30 minutes of the LT session, similar to the active TSS intervention. After 30 minutes, the stimulator unit was disconnected from the electrode leads.

Outcome Measures

Walking Assessments:

All walking-related data were captured during overground walking; participants were given the standardized instruction “walk as quickly and safely as possible”. Participants wore a gait belt during walking assessments and were guarded by a physical therapist for safety. During testing, participants used the walking assistive and orthotic devices they typically used during therapy, however no body weight support was provided during testing.

10-Meter Walk Test (10MWT). We utilized the 10MWT, which was our primary outcome measure for walking speed to assess changes in walking speed at the beginning and end of each 2-week LT block. A stopwatch was used to capture walking speed. Participants completed 3 walks in each assessment session with a 2 min rest between trials.

Additionally, spatiotemporal gait characteristics were recorded during the 10MWT using a 6-meter instrumented walkway (GAITRite, CIR Systems, Franklin, NJ, USA) positioned in the middle of the 10-meter walking path. Each walk consisted of at least 4 consecutive footfalls over the mat. Footfall data generated by the GAITRite software were used to compute step asymmetry between the stronger and weaker leg as follows: Step Length Asymmetry: $\frac{\text{larger step length}}{\text{larger step length} + \text{smaller step length}}$. Step length asymmetry was averaged across trials and used for analysis.

2-Minute Walk Test (2MWT) was used to assess changes in walking distance at the beginning and end of each 2-week LT block. Distance was measured with a measuring wheel.

Spasticity Assessments:

Pendulum test. The pendulum test, our primary measure of spasticity, was used to assess stretch-induced quadriceps reflex excitability based on first swing excursion (FSE) angle (recorded using motion capture software) wherein a larger angle indicates a greater excursion of the limb before the onset of reflex muscle contraction, and therefore less spasticity (Stillman and McMeeken 1995). Briefly, participants were positioned reclined at the edge of an adjustable height mat with both legs flexed at the knee, and with the lower leg hanging over the mat with shoes removed. Wireless sensors were strapped to both lower extremities to capture knee joint angles using inertial motion capture software (XSENS MVN, Xsens Technologies BV, Enschede, The Netherlands). Calibrated angles were verified with the leg in full extension prior

to starting the test; each leg was extended, and dropped separately. Pendulum responses in each leg were tested 3 times. For each leg, the average FSE in the 3 trials of each test session was used for analysis. To confirm stretch-induced quadriceps activation during the pendulum test, electromyographic (EMG) was concurrently monitored via electrodes (Motion Lab Systems, Baton Rouge, LA) placed over the rectus femoris muscle. EMG data were monitored using Spike software (Cambridge Electronic Design Limited, Cambridge, England). Knee angle data were analyzed off-line using customized MATLAB software (MATLAB, Mathworks).

Ankle clonus drop test (drop test). The drop test, the plantar flexor analog of the pendulum test, was used to assess stretch-induced reflex excitability in the ankle plantar flexors. The number of clonic oscillations captured using the drop test correlates with both electrophysiologic and clinical measures of spasticity (Manella, Roach et al. 2017). Participants sat upright with back support on the edge of a mat table, with shoes removed and socks left on. Wireless sensors were strapped to both lower extremities to capture ankle joint angles using inertial motion capture software (XSENS MVN, Xsens Technologies BV, Enschede, The Netherlands). The ball (metatarsal heads) of one foot was positioned on the edge of a platform (10cm height). The mat height was adjusted to ensure that the hip, knee, and ankle joints were at 90-degree angles. The participants' leg was lifted from beneath the knee until it came into contact with a T-bar positioned 10cm above the resting position of the knee. The examiner quickly released the leg allowing the forefoot to impact the edge of the platform, eliciting a quick stretch of the plantar flexors. Responses in each ankle were tested 3 times. For each leg, the number of clonic oscillations in each trial was counted off-line, and the average number of oscillations for the 3 trials of each test session was used for analysis. Soleus EMG data were concurrently monitored using Spike software (Cambridge Electronic Design Limited, Cambridge, England), and testing resumed only when the muscle had been quiet for 30s. Ankle joint oscillations were analyzed off-line using customized MATLAB software (MATLAB, Mathworks).

Modified Spinal Cord Injury – Spasticity Evaluation Tool (mSCI-SET). The mSCI-SET is a self-report measure of the effect of spasticity on 33 aspects of life. Scores range from -2 to +1; negative scores indicate problematic effects of spasticity, while positive scores indicate helpful effects of spasticity (Sweatman, Heinemann et al. 2020).

Pre/Post training Assessments

Spinal Cord Assessment Tool for Spastic Reflexes (SCATS). The SCATS was used as a clinical measure of spasticity that has been shown to be reliable and valid in persons with SCI (Benz, Hornby et al. 2005). The SCATS was performed on each leg immediately before and after every intervention session by masked clinical assessors. Assessors rated clonus, flexor spasms, and extensor spasms, on a 4-point scale for each lower extremity. For clonus and extensor spasms the scale was as follows: 0-no reaction, 1-mild lasting <3 seconds, 2- moderate lasting 3-10 seconds, and 3- severe lasting >10 seconds. The scale for flexor spasms was determined by measuring degrees of flexion at the knee and hip on the following scale: 0- no reaction, 1- mild <10 degrees, 2- moderate 10-30 degrees, 3- severe >30 degrees.

Tolerability of stimulation. During the 2-week intervention period, participants were asked to rate the tolerability of their stimulation (LT+TSS and LT+TSSsham). Using a numeric rating scale (NRS) from 0 to 10, participants were asked how tolerable the stimulation was in regard to pain, with 0 being no pain and 10 being the worst pain imaginable. Responses were taken prior to the start of the stimulation to determine baseline tolerability, and then 1 minute and 30 minutes during stimulation.

Data analysis

Data were analyzed using SPSS (version 26; SPSS Inc., Chicago, IL, USA). Numerical and ordinal data were presented as the mean(SD) and median(IQR), respectively. For spasticity measures, data in the more- and less-impaired legs (as determined by lower extremity motor score [LEMS]), were analyzed separately. Due to our small sample size, nonparametric tests were performed (Portney and Watkins 2009). Mann-Whitney U tests were conducted to examine differences between the LT+TSS and

LT+TSSsham groups in change in walking ability (speed, distance, step length asymmetry) and spasticity (pendulum test, clonus drop test, mSCI-SET) during the wash-in (LT only) period, and during the intervention (LT+TSS, LT+TSSsham) period. The Wilcoxon signed-ranks test was used to examine changes within each group during the 2 study periods. Significance was set at $\alpha = 0.05$ for all analyses. We did not adjust the significance level for multiple comparisons as our measures cannot be assumed to be independent (Hart and Bagiella 2012), and because such adjustments are known to increase the likelihood of false negatives (Type II errors) (KJ 1990, Perneger 1998, Nakagawa 2004, Hart and Bagiella 2012) which is problematic in preliminary studies. For within-group comparisons, we computed the effect sizes as these are considered more meaningful than p-values for clinical interpretation of results (Borenstein 1997, Nakagawa 2004, Lakens 2013). We computed the effect size using Hedges' *g*, as this approach is recommended for small samples (Lakens 2013). Effect sizes were interpreted per recommendations for rehabilitation studies as small effects, 0.08 to 0.15; medium effects, 0.19 to 0.36; and large effects, 0.41 to 0.67 (Kinney, Eakman et al. 2020).

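### Do the final walking and spasticity outcomes miss the sixth stimulation bout, and does that undermine the comparison with sham?

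*Combined protocol and SAP*

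**What the plan says.** The Study Design section of the combined protocol and SAP describes two blocks. For the wash-in: "For the first two weeks, participants received 6 bouts of LT". For the second block, "participants were randomized to receive 6 bouts of either 30 minutes of TSS coupled with LT or a sham-control stimulation coupled with LT".

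On the main outcomes it says: "Primary outcome assessments for walking function and spasticity were conducted at the beginning and end of each 2-week intervention block". The timing rule comes next: "The assessments at the end of each 2-week block were performed prior to the training on that day". Day-by-day measures are treated separately: "Pre-post training assessments of spasticity and assessments of tolerability (see below) were performed on each training day".

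The Intervention section confirms the dose per bout: "Stimulation was delivered for 30 minutes at the target stimulation intensity and occurred concomitantly with LT". Under Pre/Post training Assessments, the SCATS follows its own schedule: "The SCATS was performed on each leg immediately before and after every intervention session by masked clinical assessors".

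The Data analysis section compares the two arms on change within each period by Mann-Whitney tests. It adds: "The Wilcoxon signed-ranks test was used to examine changes within each group during the 2 study periods". Hedges' g is computed for the within-group comparisons.

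Three things are not stated: the bout number at which each end-of-block assessment falls, whether any training session follows the twelfth bout, and whether the end-of-wash-in assessment also serves as the baseline for the second block.

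**The concern.** If the end-of-block assessment comes before training, and the day's training is one of the 6 bouts, the last bout cannot contribute to the outcome. The final 10MWT and pendulum test (the two primary measures) would then show the effect of five stimulation bouts while a report would speak of six. The same would hold for the 2MWT and step length asymmetry, and by inference for the drop test and mSCI-SET, whose visit timing is not given separately.

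Two consequences would matter. If the effect accumulates, the contrast with sham would be smaller than a six-bout contrast, in a study that already calls itself small and preliminary and worries about false negatives. And if the end-of-wash-in assessment was taken before the sixth LT bout and reused as baseline, the intervention-period change would include one bout of LT without stimulation. The two within-group changes, and the Hedges' g for each, could then rest on different numbers of bouts without the reader knowing.

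**Working it through.** **Inputs.** 6 bouts per block and 30 minutes of TSS per active bout (Study Design; Intervention). Assessments at the start and finish of each block, the closing one before that day's training (Study Design). The document states no sample size, target effect, total dose or dose-response, so there is no figure of the plan's own to reproduce.

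**Exposure before the final assessment.**

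- Full course: 6 × 30 = 180 minutes.
- Assessed before the sixth bout: 5 × 30 = 150 minutes; 5/6 = 83.3%, leaving 1 − 5/6 = 16.7% not yet delivered.
- Assessed before a later, undocumented session: 180 minutes, nothing missing.

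**Bouts covered by each period's change.** The timing rule can mean *before the sixth bout of the block* or *before the next session after the block*. The second-block baseline can be a separate visit or the end-of-wash-in visit reused.

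| End of wash-in assessed | Final assessed | Second-block baseline | Wash-in change | Intervention change |
|---|---|---|---|---|
| before LT bout 6 | before bout 6 | separate, after LT bout 6 | 5 | 5 |
| before LT bout 6 | before bout 6 | reused | 5 | 6 (1 LT only + 5) |
| before first TSS/sham bout | after bout 6 | reused or separate | 6 | 6 |
| before first TSS/sham bout | before bout 6 | reused or separate | 6 | 5 |
| before LT bout 6 | after bout 6 | separate, after LT bout 6 | 5 | 6 |
| before LT bout 6 | after bout 6 | reused | 5 | 7 (1 LT only + 6) |

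The Study Design wording, taken literally, gives the second block its own opening assessment. That assessment follows the sixth LT bout, because all 6 fall in the first two weeks. With a separate baseline and one meaning of the timing rule for both blocks, the counts are equal: 5 and 5, or 6 and 6. Unequal counts need a reused baseline or a timing rule that means different things in the two blocks.

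**Possible loss relative to a six-bout effect.** This rests wholly on assumption. If the effect approaches a plateau exponentially with a time constant of τ bouts, the proportional loss is

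1 − (1 − exp(−5/τ)) / (1 − exp(−6/τ)).

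- τ = 1: 0.004, or 0.4%.
- τ = 3: 0.062, or 6%.
- τ = 6: 0.106, or 11%.
- Strictly linear build-up (the limit as τ grows): 0.167, or 17%.
- Plateau already reached: 0.

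**Effect on the planned tests.** In every row of the table the two arms share the same row. The Mann-Whitney comparison therefore contrasts TSS with sham after equal numbers of bouts, and its type I error is untouched. The Wilcoxon tests ask whether each group changed within a period. None compares the wash-in change with the intervention change, so no planned p-value depends on the two counts being equal.

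**The case for a change.** The strongest case for acting is that the five-bout reading is the natural one. The assessment day has training, the assessment comes first, and no session beyond the 6 + 6 is described. The fourth row of the table (6 and 5) is also quite plausible, since one visit just before the first TSS or sham bout could close the wash-in and open the intervention block. If the effect grew linearly, the standardised effect would be 5/6 of its six-bout value, and the sample size for equal power would rise by (6/5)² = 1.44. In a small study that is not trivial. Assessing after the sixth bout, before any further training, would still exclude same-session effects.

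What stands is that a reader wants the bout count. The rest does not amount to a fault in the design. The factor of 1.44 is the extreme of an assumed range that starts at no loss, and it counts as a loss only against a six-bout target the plan never sets. Moving the assessment also has a price. The battery comprises three timed walks over an instrumented walkway, a 2MWT, pendulum and drop tests on both legs with motion sensors and EMG, and a 33-item questionnaire. A separate non-training visit would add a gap after the last bout that varies between participants unless standardised, and would add a chance of missing final data. Since the document is written in the past tense, only wording could change in any case.

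**Conclusion.** The concern reads the text correctly but does not call for a change. On the natural reading, the final outcomes follow 5 of 6 bouts (150 of 180 minutes of TSS), and on the other possible reading all 6. Either way the randomised comparison is fair, because both arms are measured at the same point. The resulting estimate is the effect of the bouts completed by then. The shortfall against a six-bout effect is between 0 and 17% under the dose-response shapes assumed above, and the document contains nothing that would narrow this.

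Assessing before training is a reasonable trade-off: it gives up at most one bout of exposure to keep fatigue and acute stimulation effects out of the walking and reflex measures. The baseline question is a gap that analysts fill sensibly, by using the last assessment before the first TSS or sham bout. Giving the number of bouts behind each assessment would help readers of the within-group effect sizes, but it would alter no planned test and no result.

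This conclusion assumes that the same visit schedule was applied in both arms, as the Study Design section implies by stating one rule for all participants.

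### Step length asymmetry is formed as an unsigned ratio and then averaged over walks; if the larger side is picked in each walk, an improvement that ends near symmetry is understated

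*Combined protocol and SAP*

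**What the plan says.** Under Outcome Measures, Walking Assessments, the instrumented-walkway footfall data "were used to compute step asymmetry between the stronger and weaker leg as follows": larger step length divided by the sum of the larger and smaller step lengths. The next sentence is "Step length asymmetry was averaged across trials and used for analysis".

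The amount of data behind each value is given in two places. On the number of walks: "Participants completed 3 walks in each assessment session with a 2 min rest between trials". On the footfalls in a walk: "Each walk consisted of at least 4 consecutive footfalls over the mat". The walkway is 6 m long.

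The Data analysis section uses Mann-Whitney tests to compare the "groups in change in walking ability (speed, distance, step length asymmetry") in each period, and signed-rank tests for change within each group. The index is not the primary walking measure: "We utilized the 10MWT, which was our primary outcome measure for walking speed".

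The documents do not say when the larger side is chosen: per step pair, per walk, per session, or once per participant. The rule based on lower extremity motor score, under which "data in the more- and less-impaired legs (as determined by lower extremity motor score [LEMS]), were analyzed separately", is stated for spasticity measures only.

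**The concern.** The index cannot fall below 0.5. If it is formed in each walk, any chance difference between the legs counts upward, whichever leg happened to step longer. In a clearly asymmetric walker the same leg is longer in nearly every walk and chance differences average out. In a near-symmetric walker they do not, and the session value settles above 0.5 by an amount set by step variability.

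The analysed variable is change. A participant who starts clearly asymmetric and ends near symmetry has an almost unbiased starting value and an inflated end value, so the recorded improvement is too small. The stake is a loss of sensitivity in one of the three walking outcomes, in a study that describes its own sample as small.

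**Working it through.** **Nothing to reproduce.** The documents state no expected value, SD or power for this index.

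**Inputs from the documents.** Three walks per session; 6 m walkway; at least 4 footfalls per walk; the formula; averaging of the index over walks.

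**Inputs assumed.** Mean step 0.40 m, so 6/0.40 = 15 footfalls, 14 step lengths, 7 per leg per walk. Step-to-step SD s = 0.03 m (range 0.02 to 0.05). Correlation r between the two leg means in a walk of 0 (range -0.3 to 0.8). Larger side picked in each walk.

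**Formula.** With L and R the leg means and D = L - R,

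larger/(larger+smaller) = 0.5 + |D| / [2(L+R)], which is about 0.5 + |D|/1.6 when L+R is about 0.80 m.

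Within a walk D has SD t = s × sqrt(1/k1 + 1/k2 - 2r/sqrt(k1 k2)), where k1 and k2 are the steps per leg. If each leg is averaged over the three walks first, t is divided by sqrt(3). For a true difference d,

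E|D| = t sqrt(2/pi) exp(-d²/(2t²)) + d[1 - 2Phi(-d/t)].

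**Symmetric walker, base case.** t = 0.03 × sqrt(2/7) = 0.0160 m.
- Per-walk pick: 0.0160 × 0.798 / 1.6 = 0.0080, so the index is 0.508.
- Legs averaged first: 0.0080/sqrt(3) = 0.0046, so the index is 0.505.

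**Share of the true change recorded, base case** (true index = 0.5 + d/1.6):

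| True difference | True fall | Per-walk pick | Legs averaged first |
|---|---|---|---|
| 0.04 m to 0 | 0.025 | 0.0170/0.025 = 68% | 0.0204/0.025 = 82% |
| 0.08 m to 0 | 0.050 | (0.050-0.0080)/0.050 = 84% | (0.050-0.0046)/0.050 = 91% |
| 0.12 m to 0 | 0.075 | (0.075-0.0080)/0.075 = 89% | (0.075-0.0046)/0.075 = 94% |
| 0.04 m to 0.02 m | 0.0125 | (0.5250-0.5135)/0.0125 = 92% | over 99% |
| 0.08 m to 0.04 m | 0.025 | about 100% | about 100% |

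**Sensitivity of the 0.04 m to 0 case:**

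| Setting | Symmetric walker, per-walk / averaged first | Share kept, per-walk / averaged first |
|---|---|---|
| r = -0.3 | 0.509 / 0.505 | 64% / 79% |
| r = 0.5 | 0.506 / 0.503 | 77% / 87% |
| r = 0.8 | 0.504 / 0.502 | 86% / 92% |
| s = 0.02 m, r = 0 | 0.505 / 0.503 | 79% / 88% |
| s = 0.05 m, r = 0 | 0.513 / 0.508 | 51% / 69% |
| Only 4 footfalls (2 steps on one leg, 1 on the other), s = 0.03 m, r = 0 | 0.518 / 0.511 | 41% / 59% |

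Simulation of 400,000 sessions per setting agrees with the formula for symmetric walkers and supplies the shares kept.

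**Inflation away from symmetry.** At a true difference of 0.04 m the per-walk inflation is 0.0001 or less in the base case, about 0.001 at s = 0.05 m, and about 0.003 to 0.0035 with only 4 footfalls.

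**Cross-check.** Treating the walk-level ratio itself as normal, the base case corresponds to an SD of 0.0160/1.6 = 0.010. At that SD a true change from 0.55 to 0.50 is understated by 16%, which matches the 84% kept above. Over walk-level SDs of 0.005 to 0.04 the understatement runs from 8% to 56%.

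**Precision.** Mean change divided by its measurement SD improves by about 7% to about one third when legs are averaged first, over the settings above. This counts measurement noise only; spread between participants would dilute it.

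**The case against.** **The per-walk pick is not stated.** This is the strongest objection, and it stands. If the side was picked once per session from the session means, a symmetric walker scores 0.5046, which is already the recommended version. If the side was fixed in advance, the inflation vanishes. The averaging sentence makes the per-walk pick the natural reading but does not establish it.

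**The sizes are all assumed, and the 0.04 m case is unfavourable.** This also stands. It starts from a small asymmetry and lands exactly on symmetry. Nothing in the documents shows that participants ended there, and each training period lasted only two weeks. Larger starting differences, or end points short of symmetry, lose much less.

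Three stronger readings are tempting, and the documents do not support them.

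- A reader might infer that the formula contradicts its description, because the text names a stronger and a weaker leg while the ratio carries no leg identity. A weaker-leg share moving from 0.45 to 0.55 does score 0.55 both times. But naming the legs claims no direction, the printed formula is the operational definition, and a magnitude is a legitimate outcome. This is a matter of labelling.
- A reader might infer that the index could create a false difference between arms. A constant shift cancels; a spurious difference would require step variability to change differently by arm, and nothing in the documents suggests that.
- A reader might cite the plan's remark that "such adjustments are known to increase the likelihood of false negatives (Type II errors". It defends the absence of a multiplicity adjustment and says nothing about measurement.

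**Conclusion.** The point holds in a limited form and is minor. Taken literally, the stated order of operations (ratio in each walk, then average) understates improvement that ends near symmetry, and averaging each leg over the session first is a better method that uses the same data. In the base case the gain is from 68% to 82% of the true change for a small asymmetry that resolves completely, from 84% to 91% for one twice as large, and essentially nothing when the end point is clearly asymmetric.

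This rests on the larger side being picked per walk and on assumed step length, variability and between-leg correlation. More correlated legs shrink the effect; more variable steps or few footfalls enlarge it. It does not suggest that a reported difference between arms is spurious, and it does not touch the 10MWT.

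**What to change.** 1. State how and when the larger side was picked in the index that was analysed.
2. Average each leg's step length over all footfalls in the session's three walks, then form larger/(larger+smaller) once per session.
3. Describe the index as an unsigned magnitude of asymmetry.
4. Report the recomputed index, labelled post hoc, beside the one already analysed.

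If item 1 shows that the side was picked once per session from the session means, or fixed in advance, items 2 and 4 are not needed for this reason.

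The cost is a recalculation from footfall data already recorded. The document is written in the past tense, so the new index is unavoidably post hoc and adds one more version of a secondary result to an analysis without multiplicity adjustment. The inflation is reduced, not removed (0.508 to 0.505 in the base case). A signed weaker-leg share would avoid the inflation but should not replace the magnitude, because participants who reach symmetry from opposite sides would cancel out.
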